### 3.4. Inclusion/Exclusion Criteria:

We will use consecutive sampling to identify potential patient participants. Based on UHI patient volume and demographics, we anticipate an equal distribution of urban- and rural-dwellers and 60:40 female:male ratio. For the clinician sample, we will seek to enroll all clinicians who meet inclusion/exclusion criteria (n=5 nurses; 5 doctors).

Patient inclusion criteria include: 1. UHI patient presenting for routine or urgent outpatient visit; 2. Currently living in Uganda and not planning to travel abroad for six months; 3. Age  $\geq 18$  years; 4. Symptomatic (New York Heart Association Class II, III, or IV) HF regardless of LVEF; 5. Access to a mobile phone; 6. Basic reading skills in English, Luganda, and/or Runyankole.

Patient exclusion criteria include: 1. Life expectancy  $<$  six months; 2. Active medical condition requiring hospitalization, such as cardiac ischemia (acute electrocardiographic changes and/or positive biomarkers, if available), syncope, or significant fluid overload; 3. Pregnancy; 4. Inability to provide informed consent.

Clinician inclusion criteria include: 1. UHI staff doctor or nurse; 2. Anticipated assignment to Medly Uganda duties at least once during the study period.

Clinician exclusion criteria includes unwillingness to provide informed consent.

## 4. STATISTICAL ANALYSIS

### 4.1. Sample Size:

Sample size calculation is based on published experience with SCHFI.(68) Given a sample size of 54 patients, we can detect a mean improvement of 10 points in SCHFI (primary outcome) at six months, assuming a standard deviation of 25 for the change of score (which gives effect size of 0.4), 2-sided type I error of 0.05, and power of 0.90. Allowing for a loss of 25% during the study, the *target sample size will be 72 patients*.

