### 3.2. Study Design

This is a single-center prospective cohort study conducted at UHI. The study period is 6 months. Patient participants will have three study timepoints (Baseline, Month 3, and Month 6) while data will be collected from clinician participants only at Month 6.

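### With 54 completers and a two-sided 0.05 test, power for a 10-point change is about 0.82, not the stated 0.90

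*Combined protocol and SAP*

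**What the plan says.** Section 4.1 (Sample Size) gives the whole calculation: "Given a sample size of 54 patients, we can detect a mean improvement of 10 points in SCHFI (primary outcome) at six months". The inputs are a standard deviation of 25 for the change score, hence a standardised effect of 0.4, and "2-sided type I error of 0.05, and power of 0.90". The section then inflates for attrition ("Allowing for a loss of 25% during the study") and concludes that the "target sample size will be 72 patients".

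The design has no comparison group. Section 3.2 states: "This is a single-center prospective cohort study conducted at UHI". The powered comparison is therefore the mean within-patient change against zero. Section 4.2, written for Aim 1, names the paired t-test for changes at Months 3 and 6, with the Wilcoxon signed rank test if normality fails. The Aim 2 methods in Section 4.3 define the primary outcome as change in the SCHFI Management scale but name no test.

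**The concern.** Sample size, effect, standard deviation, alpha, sidedness and power are tied together by one formula, so once five are fixed the sixth follows. Here all six are stated, and they do not fit.

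This is the power statement for the primary outcome. If it is too high, the study is more likely than its readers believe to miss a true 10-point improvement. The error also passes into the enrolment target, because 72 is derived from 54. The section on potential challenges and alternative approaches plans to review follow-up and data completeness and to raise enrolment if needed. It gives no completer number, so Section 4.1 offers the only figure against which that need could be judged. A team that retained 54 patients would believe it had 90% power.

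**Working it through.** **Inputs, all from Section 4.1:** mean change 10; SD of change 25; d = 10/25 = 0.4; two-sided alpha 0.05; power 0.90; n = 54; loss 25%. The single-group design is from Section 3.2.

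**1. The attrition step reproduces.** 54 / (1 − 0.25) = 72, as stated.

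**2. The base figure of 54 does not.** For a one-sample (paired) mean, n = (z_alpha + z_power)² / d².
- Two-sided 0.05, power 0.90: (1.960 + 1.282)² / 0.16 = 65.67 with unrounded quantiles, so 66.
- The exact paired t-test (noncentral t, df = n − 1, noncentrality 0.4√n) gives 0.897 at n = 67 and 0.902 at n = 68, so 68.

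**3. Power at n = 54.** The noncentrality is 0.4 × √54 = 2.939.
- Normal approximation, two-sided: Φ(2.939 − 1.960) = Φ(0.979) = 0.836.
- Exact paired t, two-sided: 0.823.
- Wilcoxon signed rank, 20,000 simulated samples of normal data: about 0.81.

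The probability of missing the effect is 1 − 0.823 = 17.7% by the t-test (1.77 times the stated 10%), or 16.4% by the normal approximation (1.64 times).

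**4. What 54 completers can detect with 90% power, two-sided.**
- Normal approximation: 25 × (1.960 + 1.282) / √54 = 11.03 points.
- Exact t: d = 0.4493, and 0.4493 × 25 = 11.23 points.
- Keeping 10 points, the SD would have to be 10 / 0.4493 = 22.3 (t) or 22.7 (normal) instead of 25.

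**5. Where 54 could have come from.** Variants tried at 0.90 power:

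| Calculation | n |
|---|---|
| Two-sided, normal | 66 |
| Two-sided, exact t | 68 |
| One-sided 0.05, normal | 53.52, so 54 |
| One-sided 0.05, exact t | 55 |
| Two-sample formula, two-sided | 132 per arm |
| Two-sample formula, one-sided | 108 per arm |

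Only the one-sided normal formula, (1.645 + 1.282)² / 0.16, returns 54.

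**6. Enrolment for true 90% power at 10 points.** 68 / 0.75 = 90.7, so 91 (t); 66 / 0.75 = 88 (normal).

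**The case against.** The strongest reply accepts the arithmetic and disputes its importance. Power stays above 0.80 at the planned attrition. Aim 2 is described as preliminary, in an uncontrolled single-centre cohort, and the type I error is unaffected. If attrition is lighter, power recovers: all 72 completing would give 0.917, and 68 completing would give 0.902. These points are correct, and they are why no larger study need be demanded. They do not rescue the stated figure. The plan itself expects 25% loss, which leaves 54, whereas 68 completers out of 72 allows a loss of only 4/72, or 5.6%. A preliminary study that chooses to state alpha and power must still state them consistently.

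Three narrower points stand in part:
- The one-sided origin is inferred from a numerical match, and the match holds only for the normal formula; with the t-test, one-sided power at 54 is 0.896 and 55 are needed. The inconsistency does not depend on this explanation.
- The Aim 2 section names no test, so the t-test is carried over from Section 4.2. The normal and t calculations give 0.84 and 0.82, and the Wilcoxon test gives slightly less. None reaches 0.90.
- The passage on raising enrolment does not cite 54. Its dependence on that figure is a reasonable reading, not something the text says.

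**Conclusion.** The point holds. On Section 4.1's own inputs, 54 completers give two-sided power of 0.82 (paired t) to 0.84 (normal approximation), a shortfall of 6 to 8 percentage points from 0.90. The completer count is 12 to 14 too low for the stated power. The enrolment target is 16 (88 − 72) to 19 (91 − 72) too low at 25% loss.

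This rests on a one-sample analysis of change, as the single-cohort design implies, and on the plan's own SD of 25 and effect of 10 points. No outside figure is needed. The attrition arithmetic is sound, and the false-positive rate is not affected.

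**What to change.** Keep enrolment at 72 and correct the power sentence in Section 4.1 to say, in substance:

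> Fifty-four completers give about 82% power (paired t-test, two-sided alpha 0.05) to detect a mean change of 10 points with a standard deviation of change of 25, or 90% power to detect 11.2 points.

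This costs one sentence and a less favourable stated power. It needs no extra patients and no change to the analysis.

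If the sponsor insists on 90% power at 10 points, Section 4.1 should give 68 completers and 91 enrolled at 25% loss, and 68 should be the number used when follow-up is reviewed. The section on potential challenges says the eligible population is large enough to enrol more. If a one-sided test was in fact intended, it must be declared and justified, because the current text says two-sided.

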### 4.2. Statistical Methods for Aim 1:

This Aim focuses on a comprehensive evaluation of implementation and process outcomes for Medly Uganda at UHI. Quantitative data sources include an adapted feasibility survey exploring domains such as Acceptability and Practicality (Table 2) and app and dashboard usage data (Table 3). Qualitative data sources include SSI and dashboard content analysis (Table 2).

For *quantitative data*, descriptive statistics will be generated to characterize the feasibility, acceptability, and adoption of the app and dashboard. Mean (median) and standard deviation (range) for continuous variables and counts and proportions for categorical variables will be reported. The normality assumption of the distribution will

be checked. If the normality assumption holds, the paired t-test will be used to evaluate changes in outcomes at Months 3 and 6. Otherwise the Wilcoxon signed rank test will be performed. For the *qualitative data*, interviews will be transcribed by RAs. A coding team will code all transcripts using the constant comparative method and a thematic analysis will be done using Atlas.ti software. Merged integration will be used to synthesize quantitative and qualitative findings using the Technology

Feasibility Domain	Content Area	Data Source
Acceptability	Patients: usefulness, confidentiality, impact on self-care	SSI, survey
	Clinicians: patient safety, clinical utility	SSI, survey
Practicality	Patients: mobile phone access, intended future use of app	SSI, survey
	Clinicians: burden of alerts, impact on clinical workflow	SSI, content analysis, survey

Table 2. Feasibility domains of interest, content areas for each participant type, and data sources.

Tool	Metric	Data Source
App	Frequency of USSD sessions (initiated, completed, incomplete)	RapidPro/MOH server
	Questions per USSD session	
	Duration of USSD session	
	Status level assigned	
	Message sent	
Dashboard	System fidelity to decision tree algorithm	UHI server
	Frequency of logins, by role	
	Actions taken	
	Content entered	
	Duration of session	

Table 3. App and dashboard metrics of interest and data sources.

Acceptance Model for Resource Limited Settings (TAM-RLS), a recent adaptation of the widely used TAM. TAM-RLS was created as a framework for evaluating mobile health interventions developed for resource-limited settings.(13) Finally, a content analysis will be conducted of dashboard entries. Drs. [name], [name], and [name] will jointly support the PIs on the implementation process. Drs. [name] and [name] will oversee the quantitative methodology while Drs. [name] and [name] will oversee the qualitative methodology and integration.

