smartphones onsite to allow participants who do not have a phone with them at this time to fully participate in on-site study procedures (registration and on-boarding). There are three study timepoints for patient participants: Baseline, Month 3, and Month 6. Study procedures include multiple widely used, validated clinical measurements: Self-Care in Heart Failure Index (SCHFI), EQ-5D, Six-Minute Walk Test (6MWT), and limited transthoracic echocardiogram for measurement of Left Ventricular Ejection Fraction (LVEF). Echocardiograms will be performed by a UHI cardiologist but interpreted en bloc and blinded at study conclusion to avoid interpretation bias. At Baseline, participants will complete informed consent, register in FC, orient to the app and message content, and conduct mock sessions until comfortable using the system, as determined by RN. We will also collect weight, vital signs, and a list of prescribed medicines. Urine pregnancy test will be done on women of childbearing age. SCHFI, EQ-5D, 6MWT, and LVEF will be completed. Clinician participants will be oriented to the app, dashboard, and expectations regarding their use by the RN. At Month 3, RN will review app activity with the participant and re-educate or re-orient them to the app, as needed. SCHFI, EQ-5D, 6MWT, and LVEF will be repeated. At Month 6, SCHFI, EQ-5D, 6MWT, and LVEF will be repeated. Participants will complete a feasibility survey and the RA will conduct an SSI using an interview guide (Appendix). Since the app is used on their personal phone, they will retain this device. Following the Month 6 visit, patient participants will be able to continue using Medly Uganda, however, depending upon the funding environment, may be responsible for associated USSD and SMS costs. Upon completion of Month 6 procedures by all active patient participants, clinician participants will complete a modified feasibility survey and the RA will conduct an SSI using a different interview guide.

Procedure	Comments
SCHFI	22-item instrument validated and used in LMIC settings. (6, 34)
EQ-5D	Generic, five-item HRQoL instrument validated and used in LMIC settings and for HF.(15, 60-64)
6MWT	Reproducible, submaximal exercise test to assess functional capacity in patients with cardiopulmonary conditions, including HF. Strong, independent predictor of morbidity and mortality in patients with HF. Measured in total distance walked independently in six minutes.(65-67)

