#### **4.3. Statistical Methods for Aim 2:**

This aim focuses on the evaluation of multiple clinical outcomes of local relevance and interest, all widely used in HF outcomes research. SCHFI (v.6) assesses three self-care domains- Maintenance, Management, and Confidence-using Likert scales.(34) Each domain is scored independently and standardized to a score of 100. The recommended time interval between administration is 3 months or less. Our primary outcome is specifically change in the Management scale, as this addresses the behaviors most closely tied to our intervention: active patient decision-making to identify symptoms and take actions to minimize them. EQ-5D assesses five domains – Mobility, Self-care, Usual activities, pain/discomfort, and anxiety/depression- using Likert scales and overall health using a visual analog scale. 6MWT and LVEF are measured in meters and percentage, respectively. Frequency of acute care visits will be abstracted from UHI clinical records and recorded as number of unscheduled visits in six months. Drs. [name] and [name] will co-lead this Aim.

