#### **4.3. Potential Challenges and Alternative Approaches:**

First, participant dropout may occur due comprehension or technical challenges using the app, accessing a stable mobile network, or loss of interest. We will conduct interim analyses of follow-up rates and data completeness and adjust enrollment upward if needed. UHI has a sufficiently large eligible patient population to allow for this. Second, it is plausible that the need to enter a PIN could dissuade app use. If this is a consistent concern in Month 3 RN reviews, we will consider removing it after consultation with partners. Third, technical challenges may arise with the app or dashboard. A UHI Information Technology Specialist, already identified, will work with GoodCitizen to address such issues. Fourth, the frequency of alerts and calls could promote clinician burnout. [name] will monitor this through monthly check-ins with staff. UHI has sufficient staff to allow us to increase the number of clinician participants should this occur.

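### The likeliest analysis of the primary outcome uses only patients with both Baseline and Month 6 scores; no missing-data method covers the 25% loss allowed, and extra enrollment does not correct selection

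*Combined protocol and SAP*

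**What the plan says.** - **Primary outcome.** Section 4.3 (Statistical Methods for Aim 2): "Our primary outcome is specifically change in the Management scale". That section assigns no test to it.
- **Tests of change.** Section 4.2 (Statistical Methods for Aim 1): "If the normality assumption holds, the paired t-test will be used to evaluate changes in outcomes at Months 3 and 6", with the Wilcoxon signed rank test if normality fails. Section 4 names no other test.
- **Sample size.** Section 4.1: with 54 patients "we can detect a mean improvement of 10 points in SCHFI (primary outcome) at six months", assuming an SD of 25 for the change. It then inflates to 72: "Allowing for a loss of 25% during the study".
- **Visits.** Section 3.4 (Procedures) gives SCHFI at Baseline, Month 3 and Month 6. The patients' feasibility survey and interview take place only at Month 6.
- **Dropout.** Section 4.3 (Potential Challenges) expects that "participant dropout may occur due comprehension or technical challenges using the app, accessing a stable mobile network, or loss of interest". Its statistical response is: "We will conduct interim analyses of follow-up rates and data completeness and adjust enrollment upward if needed".
- **Not stated in Section 4.** An analysis set, a missing-data method, or a sensitivity analysis for missing scores.

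**The concern.** A paired test needs two scores from the same patient. A patient seen at Baseline and Month 3 but not at Month 6 therefore adds nothing to the Month 6 result, although the Month 3 score says something about how that patient was doing.

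If loss is related to response, the Month 6 mean change describes those who stayed and not those enrolled. It is too high if poor responders leave and too low if good responders leave. Enrolling more patients under the same loss pattern estimates the same wrong quantity more precisely. There is no control arm, so this before-after mean is the trial's main clinical figure.

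**Working it through.** **1. Is this the primary analysis?** Section 4.1 sizes the trial on a mean change at six months with an SD of change, which is a paired calculation. The Section 4.2 test compares changes at Months 3 and 6. SCHFI is measured at those visits; the survey and interview cannot show change because they occur once. App and dashboard usage data (Table 3) build up over six months and could also be compared, so the reading is the likeliest one and not certain.

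**2. The plan's own figures.** Inflation: 54/(1 - 0.25) = 72, which reproduces. Patients left out at that loss: 0.25 × 72 = 18. The 54 does not reproduce from the stated inputs: two-sided 0.05, power 0.90 and effect size 0.4 give 66 (normal) or 68 (t), and 54 gives about 82% power. That is a separate matter; 54 is used here only as the planned number of completers.

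**3. Size of the selection error.** Let f be the fraction lost, and S and L the mean changes in stayers and leavers.

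- Mean over all enrolled = (1 - f)S + fL
- Error of the completer mean = S - [(1 - f)S + fL] = f(S - L)

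With f = 0.25 and S = 10 (L is an assumption):

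| L | Mean over all enrolled | Completer mean off by |
|---|---|---|
| 0 | 7.5 | 2.5 too high |
| 10 | 10 | 0 |
| 20 | 12.5 | 2.5 too low |

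**4. Tipping point.** SE = 25/√54 = 3.40; t(0.975, 53 df) = 2.006; smallest significant mean = 2.006 × 3.402 = 6.82. A stayer gain of 10 has a 95% CI of 3.2 to 16.8. Holding the SE at 3.40, significance is lost when 10 - 0.25D = 6.82, so the stayer-leaver gap D is 12.7 and leavers average 10 - 12.7 = -2.7. For a stayer gain of 8, D = (8 - 6.82)/0.25 = 4.7, and leavers average 3.3.

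**5. Extra enrollment.** f(S - L) does not contain the number enrolled. With no true mean change over all enrolled and an assumed gap of 10 (error 2.5 points, SD 25, 25% loss), the completer test rejects at two-sided 0.05 in 11.1% of trials with 72 enrolled, 13.3% with 96 and 17.8% with 144.

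**6. Illustrative simulation.** The link strengths and correlations are assumptions; the documents give none. Loss of 25% occurs after Month 3 and depends on Month 3 change through a logistic model, log-OR 0.5 or 1.0 per 25 points. The Month 3 change in stayers is then off by 2.99 or 5.33 points, and the Month 6 completer bias is that figure times the correlation r between Month 3 and Month 6 change:

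| r | Log-OR 0.5 | Log-OR 1.0 |
|---|---|---|
| 0.2 | 0.6 | 1.1 |
| 0.5 | 1.5 | 2.7 |
| 0.8 | 2.4 | 4.3 |

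The sign follows the direction of loss. A likelihood analysis of all three visits has bias of about 0 in this scenario (-0.02 to 0.06, simulated at r = 0.5). Also at r = 0.5:

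- With no true change, a false claim of benefit (nominal 2.5%) occurs in about 6-12% of trials if poor responders leave.
- With a true gain of 10, power falls from 82% under random loss to 57-70% if good responders leave.

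**7. Where the model helps less (also r = 0.5).** If loss comes before Month 3, it removes about 48-70% of the bias. If loss depends on the Month 6 change itself, it removes about 30-38%. Under purely random loss both estimates are unbiased, and the model is slightly more precise (SD 3.25-3.29 against 3.41-3.42).

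**The case against.** The strongest reply is that nothing in the documents shows that loss will be related to response. The dropout reasons listed under Potential Challenges are mainly reasons to stop using the app, and a patient who stops dialing may still attend Month 6 and give a score. This stands: direction and size are unknown, and the bias may be zero. A reader might infer that the plan will overstate benefit because poor responders drop out. The text does not support that, and the arithmetic is symmetric.

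The result is also fairly robust at the planned effect. A 12.7-point gap, about half an SD of change, is needed to overturn a gain of 10, and an error of 2.5 points is smaller than one SE. This stands too, though the margin is much thinner at a gain of 8.

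The simulated figures depend on inputs chosen for illustration. The range of 1.5 to 2.7 points holds only at r = 0.5; letting r vary widens it to 0.6 to 4.3. The false-benefit and power figures carry the same restriction.

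Finally, this is a preliminary single-arm cohort of 72, so a long list of sensitivity analyses would be out of proportion. That is accepted, and the fix is kept short. None of these replies supplies a missing-data method or makes extra enrollment a remedy for selection.

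**Conclusion.** The point holds as a recommended change, with medium confidence. The likeliest primary analysis drops about 18 of 72 patients at the loss the plan allows, ignores their Month 3 scores, and is backed only by a measure that restores precision.

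The possible error is 0.25 times an unknown stayer-leaver difference: zero if the groups respond alike, and 2.5 points either way for a 10-point difference. The simulated 0.6 to 4.3 points is illustrative only.

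Two stronger readings should be avoided. One is that the plan formally assigns the paired test to the primary outcome: Section 4.3 (Aim 2) assigns none. The other is that a mixed model would make the estimate valid for everyone enrolled: it does so only if scores are missing at random given those observed. Neither analysis can show that the app caused the change.

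**What to change.** Add to Section 4.3 (Statistical Methods for Aim 2), for example:

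> The primary analysis is a linear mixed model for repeated measures of SCHFI Management at Baseline, Month 3 and Month 6, with visit as a fixed effect and unstructured covariance, in all enrolled patients with a baseline score. Patients who stop using the app but attend a visit are analyzed with their scores. The single primary contrast is Month 6 minus Baseline, with its 95% CI. Sensitivity analyses are (1) the paired t-test, or Wilcoxon signed rank test if normality fails, in patients with both scores; and (2) a delta-adjusted analysis that shifts imputed missing Month 6 scores in both directions, keeps values within 0-100, and reports the shift at which the conclusion changes.

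Set the range of shifts in advance and let it extend past the 12.7 points found above.

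Report the baseline and Month 3 scores of leavers beside those of stayers. Also report the number of deaths: enrollment covers "Symptomatic (New York Heart Association Class II, III, or IV) HF regardless of LVEF", so some are possible although a life expectancy under six months is an exclusion, and the model implicitly extrapolates scores after death.

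**Cost.** SAP wording and slightly more analysis work; all three visits are already planned, so no new data are needed. The mixed model is a reasonable choice and not the only one. Its downside is reliance on missing at random: bias is reduced but not fully removed if loss comes before Month 3 or depends on the unseen Month 6 score, which is why the shift analysis is included.
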